#### 4.0 Treatment Plan

##### 4.1 Treatment Dosage and Administration

For this protocol, the term “treatment” refers to ceritinib. The dose and schedule are listed under table 4-1.

Each cycle of therapy will be 28 days long. A completed cycle will be 28 days of once daily continuous treatment. Day 1 will be the first day that ceritinib is taken, and the last day of a completed treatment

cycle will be day 28. All doses prescribed to and taken by patients, any dose adjustments and interruption or discontinuations will be recorded in the clinical trial record.

**Table 4-1 Dose and treatment schedule**

Study treatments	Pharmaceutical form and route of administration	Dose	Frequency and/or Regimen
Ceritinib	Hard gelatin capsule for oral use	450 mg (3 x 150 mg capsule)	Once daily (28-day cycle)

#### 4.1.1 Dosing regimen

Patients on this trial will begin therapy on day 1 of Cycle 1 with the first administration of ceritinib.

##### 4.1.1.1 Ceritinib

Patients will self-administer the doses of ceritinib for the cycle.

Ceritinib will be administered orally once daily at a dose of 450 mg ( 3 capsules of 150mg ceritinib) on a continuous dosing schedule. The investigator must instruct the patient to take the ceritinib treatment exactly as prescribed.

- Patients should take ceritinib once daily at approximately the same time each day, in the morning, afternoon, or evening.
- Patients should take ceritinib with food.
- Each dose of ceritinib should be taken with a glass of water and consumed over as short a time as possible (i.e., not slower than 1 capsule every 2 minutes).
- For patients with a gastrostomy tube who are unable to swallow capsules, patient will be instructed on how to prepare mixture. For patients that are unable to swallow capsules, administration can occur through a nasogastric (NG) or gastric (G) tube:
  1. Put on gloves and mask before opening containers. Take the appropriate number of capsules that are needed, out of the containers.
  2. Place a glass bowl in an area with smooth surfaces that is easy to clean.
  3. Carefully open each capsule, one at a time, and pour or tip the contents out of each capsule in the glass bowl.
  4. Carefully check to make sure that both parts of each capsule are empty. Some of the contents may stick to the inside of the capsules. If this happens, use a toothpick (or similar tool) to remove the stuck contents into the glass bowl; work over the bowl.
  5. Fill the glass bowl with at least 40 mL (eight teaspoons) of water. If taking a dose that is 200 mg or less, then use at least 20 mL (four teaspoons of water).
  6. Mix the drug powder with water carefully with the spoon.
  7. Put the end of the syringe in the glass bowl and slowly pull back on the plunger drawing the mixture into the syringe.
  8. Make sure patient is sitting relatively upright, connect the syringe to the patient's NG or G-tube and empty the mixture by slowly pushing the plunger into the syringe until all contents are empty.
  9. Repeat steps 7-8 if necessary, making sure the entire dose is administered.
  10. Once the entire dose is given, rinse the tube by syringing in 20 mL (four teaspoons) twice. If dose is 200 mg or less, then use at least 10 mL (two teaspoons) of water twice for rinsing.
  11. Dispose empty capsule shells, mask and gloves as per the hospital or institutions' guidelines

If vomiting occurs during the course of treatment, no re-dosing of the patient is allowed before the next scheduled dose.

Patients should be instructed not to make up missed doses or partial doses (i.e., when the entire dose is not taken as instructed). A missed or partial dose will be defined as a case when the full dose is not taken within 8 hours after the approximate time of the usual daily dosing. That day's dose (or partial remaining dose) should be omitted, and the patient should continue treatment with the next scheduled dose on the following day. The patient should record this in the medication diary.

#### 4.1.2 Treatment duration

Patients will continue ceritinib treatment until they experience any of the following:

- Disease progression not amenable to SABR and necessitating change in systemic therapy determined by the treating physician.
- Unacceptable toxicity that precludes further treatment.
- Start of a new anti-cancer therapy.
- Pregnancy.
- Treatment is discontinued at the discretion of the investigator or patient.
- Lost to follow-up.
- Death.
- Completed.

#### 4.2 Dose escalation guidelines

No doses escalation will be permitted on this study.

#### 4.3 Dose modifications

For patients who do not tolerate the protocol-specified dosing schedule, dose adjustments are permitted in order to allow the patients to continue the ceritinib treatment. Any changes in ceritinib administration will be recorded in the clinical trial record.

##### General guidelines for dose modifications

- For grade 1 and tolerable grade 2 treatment-related toxicities, patients are encouraged to continue at the current dose of study treatment. For intolerable grade 2 treatment-related toxicities, dosing should be interrupted until resolution to grade 1 or lower followed by dose reduction to the next dose level.
- For grade 3 or grade 4 treatment-related toxicity that is not considered by the investigator to be life-threatening, patients should interrupt study treatment until resolution to grade 1 or lower; then study treatment may continue following a dose reduction to the next dose level, if, in the opinion of the Investigator, the patient continues to experience clinical benefit. For any grade 3 or 4 treatment-related toxicity that is considered by the investigator to be life-threatening, permanently discontinue study treatment.

More detailed ceritinib dose modification guidelines are described in Section 4.3.1 respectively for selected toxicities.

All dose modifications, interruptions or discontinuations must be based on the worst preceding toxicity as graded by the NCI Clinical Toxicity Criteria version 4.03.

Patients whose treatment is interrupted or permanently discontinued due to an AE must be followed until resolution or stabilization of the event. Patients requiring interruptions greater than 1 cycle (28 days)

should be discontinued from ceritinib treatment unless the treating physician and Principle investigator agree that the patient should resume treatment.

All patients will be followed for safety until 30 days after the last dose of ceritinib.

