#### Ceritinib during stereotactic radiation:

Currently there are limited data about the safety of concurrent ceritinib and stereotactic radiation, though studies are ongoing. If there is a concern for the safety of the patient, ceritinib will be held for 3

days prior to and 3 days after the stereotactic radiation. The total expected duration of the stereotactic radiation is expected to range between 1-5 treatments, generally not exceeding 21 days from first to last radiation therapy.

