### **5.2.3 End of treatment visit including study completion and premature withdrawal**

#### **5.2.3.1 End of Phase Disposition**

Patients will be evaluated upon discontinuation of the ceritinib by a clinic visit. At that time all assessments listed for End Of Treatment will be performed. A note will be entered into the clinical trial record will be completed, giving the date and reason for stopping the ceritinib treatment.

At a minimum, all patients who discontinue ceritinib treatment, including those who refuse to return for a final visit, will be contacted for safety evaluations during the 30 days following the last dose of treatment.

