### 6.1.6 Progression-Free Survival

Progression Free Survival will be the primary endpoint for this study. If oligoprogression occurs that is amenable to repeat treatment with SABR, the ceritinib will be held and SABR therapy delivered. If the treating oncologist then feels the patient would benefit from continuing the ceritinib that will be permitted. The patient will however be deemed as having progressed even if ceritinib is resumed.

After the initial SABR to persisting lesions if new lesions appear or if existing lesions enlarge but are NOT amenable to SABR (necessitating a change in systemic therapy), the patient will have completed the therapeutic portion of the study.

Time to 2nd SABR is defined as the duration of time from the start of treatment to the time of development of new or enlarging lesions that are amenable to SABR and the progression does not require a discontinuation of ceritinib.

Time to 3rd SABR is defined in patients who have already received two rounds of SABR while on this study as the duration of time from the start of treatment to the time of development of new or enlarging lesions that are amenable to SABR and the progression does not require a discontinuation of ceritinib.

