#### 8.3.1 Ceritinib during SABR

It is not expected ceritinib and SABR would have significant toxicity if given concurrently. However to minimize risk to the patient, ceritinib will be held for 72 hours before the first radiation treatment and resumed 72 hours after the last radiation dose. While radiation is being delivered, concurrent treatment with ceritinib is not allowed.

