##### Prescription Dose

Number of Fractions	Total Cumulative Dose Encompassing 95% of Planning Target Volume		
	Protocol Compliant	Variation Acceptable	Deviation Unacceptable
1	21-27 Gy	<21 Gy but $\geq$ 16 Gy	<16 Gy or >27 Gy
3	26.5-33 Gy	<26.5 Gy but $\geq$ 24.5 Gy	<24.5 Gy or >33 Gy,
5	30-37.5 Gy	$\geq$ 28 Gy, <30 Gy	<28 Gy or >37.5 Gy,

Treatment may be delivered on consecutive days with 18 hours between fraction or every other day as deemed appropriate by the treating Radiation Oncologist.

If there is residual disease not amenable to SABR fractionation schemes proposed in the study, especially for bulky hilar or mediastinal disease, a fractionation schema of 45 Gy in 15 fractions may be employed, with adherence to standard normal tissue constraints outlined in the trial. This treatment will be delivered daily for three weeks.

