##### **9.10.2.2 Adverse events (AEs)**

Summary tables for adverse events (AEs) will include only AEs that started or worsened during the on-treatment period, the treatment-emergent AEs. However, all safety data (including those from the pre and post-treatment periods) will be listed and those collected during the pre-treatment and post-treatment period are to be flagged.

The incidence of treatment-emergent adverse events (new or worsening from baseline) will be summarized by system organ class and or preferred term, severity (based on CTCAE grades), type of adverse event, relation to study treatment by

Deaths reportable as SAEs and non-fatal serious adverse events will be listed by patient and tabulated by type of adverse event and.

Specific safety event categories (SEC) will be considered. Such categories consist of one or more well-defined safety events which are similar in nature and for which there is a specific clinical interest in connection with the study treatment(s).

For each specified category, number and percentage of patients with at least one event per category will be summarized.

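### Routine safety follow-up is counted from the last ceritinib dose only, so when ceritinib is not resumed after SABR it ends about 6 to 27 days after the last fraction, depending on the course

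*Combined protocol and SAP*

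**What the plan says.** **The window.** Section 4.3 (General guidelines for dose modifications) states: "All patients will be followed for safety until 30 days after the last dose of ceritinib". Section 5.2.3.1 says that patients who stop ceritinib, including those who decline a final visit, "will be contacted for safety evaluations during the 30 days following the last dose of treatment". Section 4.1 fixes the meaning of that last word: the term treatment "refers to ceritinib. The dose and schedule are listed under table 4-1". SABR is not part of it.

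**The hold.** Under Section 8.3.1, "ceritinib will be held for 72 hours before the first radiation treatment and resumed 72 hours after the last radiation dose". Sections 1.4 and 2.2.1 give the same three days on either side.

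**The length of radiation.** Section 1.3.3 expects one to five treatments, "generally not exceeding 21 days from first to last radiation therapy". Section 8.3.2 also allows 45 Gy in 15 fractions for residual disease unsuited to the main schemes: "This treatment will be delivered daily for three weeks".

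**Resumption.** Section 1.4 expects ceritinib to continue after radiation. For oligoprogression treated with repeat SABR, Section 6.1.6 leaves it open: "If the treating oncologist then feels the patient would benefit from continuing the ceritinib that will be permitted". Sections 2.2.1 and 9.3.1 do the same.

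**The tables and later contacts.** Section 9.10.2.2 says that the adverse event summaries "will include only AEs that started or worsened during the on-treatment period". That period is not defined relative to SABR. After the end of treatment, Section 5.1.16 provides for survival status and new therapy only, and the long-term column of Table 5-1, every three months, marks only the survival assessment.

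**The concern.** Sections 2.0 and 9.1 set out to show that ceritinib followed by SABR is safe. A window counted from the drug serves that aim while the patient goes back on the drug. If ceritinib is held for SABR and never restarted, the last dose comes before the first fraction, and the hold and the whole radiation course use up follow-up time.

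New radiation events that begin after the window closes have no scheduled contact at which they would be found. If they do come to light, they may fall outside the summary tables. Section 9.3 compares toxicity rates with historical controls by Fisher's exact test. The planned cohorts have 18 and 15 patients, so one affected patient who is not counted lowers a rate by 1/18 = 5.6 or 1/15 = 6.7 percentage points. Any such loss would make the combination look safer.

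**Working it through.** The plan gives no figure for follow-up after the last fraction, so there is none to reproduce. The check is a count of days from the plan's own numbers.

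**Inputs**
- Window: W = 30 days from the last ceritinib dose (Sections 4.3 and 5.2.3.1).
- Last dose to first fraction: h = 3 days (Sections 1.4, 2.2.1 and 8.3.1).
- First to last fraction: s days. Section 8.3.2 allows 1, 3 or 5 fractions on consecutive or alternate days, and 15 daily fractions over three weeks. Section 8.7.1 allows intracranial sessions spread over 14 days. Section 1.3.3 gives 21 days as the general upper figure.

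**Formula when ceritinib is not resumed**

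Days of follow-up left after the last fraction = W − h − s.

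| Course | s | Days left |
|---|---|---|
| 1 fraction | 0 | 30 − 3 − 0 = 27 |
| 3 fractions, consecutive | 2 | 30 − 3 − 2 = 25 |
| 5 fractions, consecutive | 4 | 30 − 3 − 4 = 23 |
| 5 fractions, alternate days | 8 | 30 − 3 − 8 = 19 |
| Intracranial sessions over 14 days | 14 | 30 − 3 − 14 = 13 |
| 15 fractions, weekdays | 18 | 30 − 3 − 18 = 9 |
| 21 days first to last | 21 | 30 − 3 − 21 = 6 |

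If three full calendar days are skipped, h = 4 and every result falls by one day, giving a range of 5 to 26. Section 1.3.3 states 21 days as a general limit, not a fixed one, so a longer course would leave less.

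**When ceritinib is resumed**

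The last dose is then at least 3 days after the last fraction, so the window closes at least 3 + 30 = 33 days after it. The gap exists only without resumption.

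**Is non-resumption foreseen?**

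Yes, in two places. Resumption after SABR for oligoprogression is discretionary. Section 4.3 also calls for discontinuation after interruptions of more than 28 days unless the treating physician and principal investigator agree otherwise. A 21-day course with both holds takes 3 + 21 + 3 = 27 days, so a slip of two days (29) passes that limit.

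**The case against.** The strongest reply is that the plan has other safeguards and that the gap is an exception.

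- **Not every safety rule is tied to ceritinib.** A reader might infer that all safety capture stops with the drug. It does not. Section 7.2 follows any existing adverse event, related or not, to resolution, a satisfactory explanation or death. Sections 7.2.2 and 7.2.2.1 send all local serious events to the DSMC with no stated 30-day limit. Section 7.3 counts from the last dose of protocol treatment and keeps later events reportable if attributed to the agents, without saying whether SABR is either. This stands. It limits the gap mainly to new-onset, non-serious radiation events. It does not create a contact at which later events would be sought.
- **Late events are not discarded.** Sections 9.10.2.1 and 9.10.2.2 list and flag post-treatment data. This stands, but listed events do not enter the summaries.
- **Resumption is the expected course.** Section 1.4 says so, and Section 6.1.6 defines time to a further SABR course by progression that does not require stopping ceritinib. This stands as to frequency. Discretion remains, so the case can occur.
- **Some routes add nothing.** After voluntary withdrawal no more data are collected (Section 5.2.3.2), so a longer window would not help. An event that causes ceritinib to stop is already followed under Section 4.3. Both points stand.
- **Six days is the extreme.** Also true. The usual one to five fractions leave 19 to 27 days.

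**Conclusion.** The point holds in a narrow form. Routine follow-up for new events has no anchor at the last SABR fraction. When ceritinib is held for SABR and not resumed, it ends about 19 to 27 days after the last fraction for one to five fractions on consecutive or alternate days, about 9 days for the 15-fraction weekday course, and about 6 days for a 21-day course.

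This assumes that the three-day hold is applied. Section 1.3.3 makes the hold depend on a safety concern, whereas Sections 1.4, 2.2.1 and 8.3.1 make it the rule.

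Two stronger readings are tempting and are not supported:
- A reader might size the problem from early progression. With exponential times and the historical medians of 10 and 7 months, 1 − 0.5^(3/10) = 19% and 1 − 0.5^(3/7) = 26% of patients still at risk would progress within three months. These are progression rates. Progression need not end ceritinib here, and the documents give no rate of non-resumption.
- A reader might conclude that the reported toxicity will be too low. The direction of any loss is clear, but nothing in the documents shows how many events, if any, would be missed.

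The case for change rests on the stated safety objective and the low cost, not on a demonstrated bias.

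**What to change.** 1. End both the safety follow-up window and the on-treatment period for adverse events 30 days after the last ceritinib dose or the last SABR fraction, whichever is later.
2. Use that anchor in Sections 4.3, 5.2.3.1, 7.3, 9.10.2.1 and 9.10.2.2. In Section 7.3, say whether SABR counts as protocol treatment and as an agent.
3. At the three-monthly contact already scheduled in Table 5-1, ask about grade 3 or higher events attributed to radiation.
4. Reconcile Section 1.3.3 with Sections 1.4, 2.2.1 and 8.3.1 on whether the ceritinib hold is conditional or mandatory, since the day count depends on it.

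The cost is a wording amendment, one added question at an existing contact, and slightly more adverse event data entry. Items 1 to 3 change no dose, schedule or treatment rule.

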#### 4.3.1 Dose modification and dose delay of Ceritinib

Guidelines for dose interruptions and re-initiation of ceritinib treatment (with or without dose reduction) are described in Table 4-2. Dosing adjustment guidelines are in Table 4-3

**Table 4-2 Dose reduction steps for ceritinib**

Ceritinib dose levels	Dose* and schedule
Starting dose level	450 mg QD continuously
Dose level - 1	300 mg QD continuously
Dose level – 2**	150 mg QD continuously

\*Dose reduction will be based on the worst preceding toxicity as per NCI-CTCAE version 4.03.

\*\*Dose reduction below 150 mg/day is not allowed. If a dose reduction below 150 mg/day is required, the patient will be permanently discontinued from ceritinib.

**Table 4-3 Criteria for interruption and re-initiation of Ceritinib treatment**

Worst toxicity (CTCAE 4.03 Grade)*	Dose Modifications for Ceritinib
HEMATOLOGICAL	
Neutropenia (ANC)	
Grade 1 (ANC < LLN - $1.5 \times 10^9/L$ )	Maintain dose level
Grade 2 (ANC < 1.5 and $\geq 1.0 \times 10^9/L$ )	Maintain dose level
Grade 3 (ANC < 1.0 and $\geq 0.5 \times 10^9/L$ )	Omit dose until resolved to $\leq$ Grade 2, then: If resolved in $\leq 7$ days, then maintain dose level If resolved in $> 7$ days, then $\downarrow$ 1 dose level
Grade 4 (ANC < $0.5 \times 10^9/L$ )	Omit dose until resolved to $\leq$ Grade 2, then: If resolved in $\leq 7$ days, then maintain dose level If resolved in $> 7$ days, then $\downarrow$ 1 dose level
Febrile neutropenia (ANC < $1.0 \times 10^9/L$ , with a single temperature of $\geq 38.3$ °C or a sustained temperature of $\geq 38$ °C for more than one hour )	Omit dose until clinically resolved and neutropenia $\leq$ Grade 2, then $\downarrow$ 1 dose level

Worst toxicity (CTCAE 4.03 Grade)*	Dose Modifications for Ceritinib
Thrombocytopenia	
Grade 1 (PLT < LLN - 75 x 10  /L)	Maintain dose level
Grade 2 (PLT < 75 and ≥ 50 x 10  /L)	Maintain dose level
Grade 3 (PLT < 50 and ≥ 25 x 10  /L)	Omit dose until resolved to ≤ Grade 2, then: If resolved in ≤ 7 days, then maintain dose level If resolved in > 7 days, then ↓ 1 dose level
Grade 4 (PLT < 25 x 10  /L)	Omit dose until resolved to ≤ Grade 2, then ↓ 1 dose level
HEPATIC	
alkaline phosphatase and/or Gamma-glutamyl transpeptidase (GGT)	
Isolated elevations of any grade	Maintain dose level
Total Bilirubin** (for patients with Gilbert Syndrome these dose modifications apply to changes in direct (conjugated) bilirubin only)	
Grade 1 (> ULN and ≤ 1.5 x ULN)	Maintain dose level with liver function test (LFTs)*** monitored as per protocol
Grade 2 (> 1.5 and ≤ 3.0 x ULN) with ALT or AST ≤ 3.0 x ULN	Omit dose until resolved to ≤ Grade 1, then: If resolved in ≤ 7 days, then maintain dose level If resolved in > 7 days, then ↓ 1 dose level
Grade 3 (> 3.0 and ≤ 10.0 x ULN) with ALT or AST ≤ 3.0 x ULN	Omit dose until resolved to ≤ Grade 1, then: If resolved in ≤ 7 days, ↓ 1 dose level If resolved in > 7 days discontinue patient from ceritinib
Grade 4 (> 10.0 x ULN)	Permanently discontinue patient from ceritinib
AST or ALT	
Grade 1 (> ULN and ≤ 3.0 x ULN)	Maintain dose level with LFTs*** monitored per protocol
Grade 2 (> 3.0 and ≤ 5.0 x ULN) without total bilirubin elevation to > 1.5 x ULN	Omit dose until resolved to ≤ Grade 1, then If resolved in ≤ 7 days, then maintain dose level If resolved in > 7 days, then ↓ 1 dose level
Grade 3 (> 5.0 and ≤ 20.0 x ULN) without total bilirubin elevation to > 1.5 x ULN	Omit dose until resolved to ≤ Grade 1, then If resolved in ≤ 7 days, then maintain dose level If resolved in > 7 days, then ↓ 1 dose level
Grade 4 (> 20.0 x ULN) without bilirubin elevation to > 2.0 x ULN	Omit dose until resolved to ≤ Grade 1, then ↓ 1 dose level
AST or ALT and concurrent Total Bilirubin	
AST or ALT > 3.0 x ULN with total bilirubin > 2.0 x ULN in the absence of cholestasis or hemolysis	Permanently discontinue patient from ceritinib

Worst toxicity (CTCAE 4.03 Grade)*	Dose Modifications for Ceritinib
RENAL	
Serum creatinine	
Grade 1 (>1 and ≤1.5 x baseline; > ULN and ≤1.5 x ULN)	Maintain dose level
Grade 2 (>1.5 and ≤3.0 x baseline; >1.5 and ≤3.0 x ULN)	Omit dose until resolved to ≤ Grade 1, then: If resolved in ≤ 7 days, then maintain dose level If resolved in > 7 days, then ↓ 1 dose level
Grade 3 (>3.0 x baseline; >3.0 and ≤6.0 x ULN)	Omit dose until resolved to ≤ Grade 1, then ↓ 1 dose level
Grade 4 (> 6.0 x ULN)	Permanently discontinue patient from ceritinib
GASTROINTESTINAL	
Diarrhea****	
Grade 1 (despite maximal anti-diarrheal medication)	Maintain dose level but adjust anti-diarrhea treatment (may change anti-diarrhea treatment)
Grade 2 (despite maximal anti-diarrheal medication)	Omit dose until resolved to ≤ Grade 1, then maintain dose level. If diarrhea returns as ≥ Grade 2, then suspend dose until resolved to ≤ Grade 1, then ↓ 1 dose level
Grade 3 (despite maximal anti-diarrheal medication)	Omit dose until resolved to ≤ Grade 1, then ↓ 1 dose level
Grade 4 (despite maximal anti-diarrheal medication)	Omit dose until resolved to ≤ Grade 1, then ↓ 1 dose level
Nausea*****	
Grade 1 (despite standard anti-emetics)	Maintain dose level but adjust anti-emetic treatment
Grade 2 (despite standard anti-emetics)	Maintain dose level but adjust anti-emetic treatment
Grade 3 (despite standard anti-emetics)	Omit dose until resolved to ≤ Grade 1, then ↓ 1 dose level
Vomiting*****	
Grade 1 (despite standard anti-emetics)	Maintain dose level but adjust anti-emetic treatment
Grade 2 (despite standard anti-emetics)	Omit dose until resolved to ≤ Grade 1, then maintain dose level. If vomiting returns as ≥ Grade 2, then suspend dose until resolved to ≤ Grade 1, then ↓ 1 dose level
Grade 3 (despite standard anti-emetics)	Omit dose until resolved to ≤ Grade 1, then ↓ 1 dose level
Grade 4 (despite standard anti-emetics)	Omit dose until resolved to ≤ Grade 1, then ↓ 1 dose level
METABOLIC	
Any Grade hypophosphatemia	Treatment with phosphate supplements as clinically indicated and maintain dose level
Hyperglycemia	

Worst toxicity (CTCAE 4.03 Grade)*	Dose Modifications for Ceritinib
Persistent hyperglycemia (glucose > 250 mg/dL despite optimal anti-hyperglycemic therapy)	Omit dose until hyperglycemia is adequately controlled then resume ceritinib at ↓ 1 dose level If adequate hyperglycemic control cannot be achieved with optimal medical management permanently discontinue patient from ceritinib.
GENERAL DISORDERS	
Fatigue (asthenia)	
Grade 1	Maintain dose level
Grade 2	Maintain dose level
Grade 3	If grade 3 fatigue resolves in ≤ 7 days, maintain dose level If grade 3 fatigue lasts > 7 days, omit dose until resolved to ≤ Grade 2 and then ↓ dose level
CARDIAC INVESTIGATIONS	
Electrocardiogram QT corrected (QTc) interval prolonged	
Grade 1 (QTc 450-480 ms)	Maintain dose level
Grade 2 (QTc 481-500 ms)	Maintain dose level
Grade 3 (QTc ≥ 501 ms on at least two separate ECGs)	When QTc ≥ 501 ms is identified at the site, interrupt ceritinib treatment and perform the following: Perform an analysis of serum potassium, calcium, phosphorus, and magnesium, and if below lower limit of normal, correct with supplements to within normal limits. Review concomitant medication usage for the potential to inhibit CYP3A4/5 and/or to prolong the QT-interval. Check compliance with correct dose and administration of ceritinib. Perform a repeat ECG within one hour of the first QTc of ≥ 501 ms. If QTc remains ≥ 501 ms, repeat ECG as clinically indicated, but at least once a day until the QTc returns to < 501 ms. If QTc returns to ≤ grade 1 (< 481 ms), ceritinib will be reduced by 1 dose level (i.e., 600 mg QD or lower). Repeat ECG in 24 hours, or less, as clinically indicated; continue monitoring as clinically indicated until QTc < 481 ms

Worst toxicity (CTCAE 4.03 Grade)*	Dose Modifications for Ceritinib
	
Repeat ECGs 7 days and 14 days (and then every 21 days) after dose resumption for all patients who had therapy interrupted due to QTc ≥ 501 ms.
 
If QTc of ≥ 501 ms recurs, interrupt ceritinib treatment. If QTc returns to ≤ grade 1 (< 481 ms), ceritinib may be reduced again by 1 dose level (i.e., 450 mg QD or 300mg QD). Repeat ECGs as described above.
 
If QTc of ≥ 501 ms recurs after 2nd dose reduction for QTc prolongation, the patient must be discontinued from study.
 
QTc of >480 ms should be reported as an adverse event (AE)

Grade 4 (QTc ≥ 501 or > 60ms change from baseline and Torsades de pointes or polymorphic ventricular tachycardia or signs/symptoms of serious arrhythmia)	Permanently discontinue patient from ceritinib
PULMONARY	

Notes:
 
 
Withhold ceritinib for acute onset of new or progressive unexplained pulmonary symptoms, such as dyspnea, cough and fever and during diagnostic workup for pneumonitis/ILD.
 
During evaluation of potential grade 2, 3, and 4 pneumonitis, if an infectious etiology is confirmed (i.e., pneumonia) and pneumonitis is excluded, then consider resuming ceritinib at current dose level after the pneumonia resolves.
 
	
PNEUMONITIS	
Any Grade treatment-related ILD/pneumonitis	Permanently discontinue patient from ceritinib.
BRADYCARDIA	
Grade 1	
Omit dose until recovery to asymptomatic bradycardia or to a heart rate ≥ 60 bpm
 
Evaluate concomitant medications known to cause bradycardia and adjust the dose of ceritinib

Grade 2	
Omit dose until recovery to asymptomatic bradycardia or to a heart rate ≥ 60 bpm
 
Evaluate concomitant medications known to cause bradycardia and adjust the dose of ceritinib

Grade 3 Grade 4 (in patients taking a concomitant medication also known to cause bradycardia or a medication known to cause hypotension)	
Omit dose until recovery to asymptomatic bradycardia or to a heart rate ≥ 60 bpm
 
If the concomitant medication can be adjusted or discontinued, resume ceritinib at ↓ 1 dose level with frequent monitoring

Grade 4 (in patients who are not taking a concomitant medication also known to cause bradycardia or known to cause hypotension)	Permanently discontinue ceritinib

Worst toxicity (CTCAE 4.03 Grade)*	Dose Modifications for Ceritinib
PANCREATIC	
Amylase and/or lipase elevations (in the absence of clinical symptoms)	
Grade 1 (> ULN and ≤1.5 x ULN)	Maintain dose level
Grade 2 (>1.5 - 2.0 x ULN)	Maintain dose level
Grade ≥3 (> 2.0 x ULN)	Omit dose until resolved to ≤ Grade 1, then ↓ 1 dose level
Note: Withhold ceritinib for acute onset of new or progressive unexplained abdominal symptoms, such as severe pain or vomiting; perform diagnostic procedures (e.g., abdominal CT scan or ultrasound) to exclude pancreatic pathology.	

* Common Terminology Criteria for Adverse Events (CTCAE) version 4.03. All dose modifications should be based on the worst preceding toxicity.
 
** If Grade 3 or 4 hyperbilirubinemia is due to the indirect (non-conjugated) component only, and hemolysis as the etiology has been ruled out as per institutional guidelines (e.g., review of peripheral blood smear and haptoglobin determination), then ↓ 1 dose level and continue treatment at the discretion of the Investigator.
 
***LFTs include albumin, ALT, AST, total bilirubin (fractionated if total bilirubin > 2.0 x ULN), Alkaline phosphatase and GGT.
 
**** Dose modifications apply to patients who experience diarrhea despite appropriate antidiarrheal medication. This medication should be started at the first sign of abdominal cramping, loose stools or overt diarrhea (see Section 4.3.2.5).
 
***** Dose modifications apply to patients who experience nausea and/or vomiting despite appropriate antiemetic medication. This medication should be started at the first sign of nausea and/or vomiting (see Section 4.3.2.6).
	

